8.3.16 Visit SC – Screening (Day -28 to 0)

Only patients who have already agreed to undergo non-penetrating glaucoma surgery will be approached by the trial team about participation in the study.

At the screening visit (SC), the Investigator will conduct the informed consent process (Section 12.1), ensuring that the subject has signed and received a copy of the patient informed consent (PIC) form before any study specific procedures are conducted. Once the PIC is signed, the subject will be assigned a patient number (Section 8.3.9) and the Investigator will determine if the subject meets the eligibility criteria, surgery (V01) will be scheduled and the sponsor will be informed.

In addition, the following procedures will be performed at the screening visit:

- Collection of background information about the subject including: demographics, medical history with prior treatments and current medications and indication for non-penetrating glaucoma surgery.
- Pregnancy test, when applicable
- Vision-related Quality of Life (VqoL) questionnaire
- Visual acuity (ETDRS)
- External eye photography
- Anterior Segment assessments (slit-lamp biomicroscopy, AS-OCT, gonioscopy)
- Posterior Segment assessments (biomicroscopy, PS-OCT and fundus photography)
- IOP measurement with GAT and if available DCT
- Instruct subjects on the need to report as soon as possible any SAEs occurring at any time throughout the study (starting from Visit 02 surgery)
- Complete the CRF.

8.3.17 Surgery, Visit 01 (Day 0)

The following procedures may be carried out up to one day before surgery (in subjects already hospitalized for the surgery) or prior to surgery on the day of surgery:

• Verify that the subject continues to meet eligibility criteria

- For female subjects of childbearing potential: collect urine for pregnancy test. A test done within 24 hours prior to surgery must be negative
- Perform external eye photography

The following procedures are to be performed on the day of the surgery:

- Updating medical history (up to start of ARGOS-SC implantation)
- Recording of concomitant medications, device deficiencies or malfunctions (including those detected during device preparation) and any Aes (starting from the point of inclusion/signing of the informed consent)
- Non-penetrating glaucoma surgery and ARGOS-SC pressure sensor implantation (described in Section 8.3.12)
- Completion of the implantation procedure questionnaire (surgeon) and the CRF
- Complete the patient inclusion form and fax it to the sponsor
- Instruct subjects on the need to immediately report any SAE that may occur at any time during the study.
- Schedule Visit 2 (V02).

The duration of the subject's hospitalization following surgery is at the discretion of the Investigator. Durations of up to 6 days will not be considered to be SAEs.

8.3.18 Follow-up visits (V02 to V09)

Procedures to be conducted at the early post-surgical visits include:

- Recording of Aes/SAEs/ADEs/SADEs, concomitant medications and device malfunctions
- VqoL questionnaire (V06, V07, V09)
- User acceptance questionnaire (investigator) (V09)
- User acceptance questionnaire (patient) (V09)
- Visual acuity (ETDRS)
- External eye photography (V04-V09)
- Heidelberg Engineering ANTERION[®] (optional V04-V09)
- Perimetry (V06, V07, V09)

- Anterior Segment assessments: slit-lamp biomicroscopy, AS-OCT (V04-V06), gonioscopy (V06, V07, V09)
- Posterior Segment assessments: biomicroscopy, PS-OCT (V06, V07, V09), fundus photography (V06, V07, V09)
- IOP Measurement: GAT and ARGOS-SC. Optional, if available V05 V09 Pascal DCT;
 Optional: 24-hour measurements inpatient with ARGOS-SC and GAT (V06, V07, V09)
- Instruction of subjects on the use of the MESOGRAPH and Multiline Connector
- At V02, provide the patient with a MESOGRAPH and Multiline Connector for home-use for the rest of the study. Patient should bring both devices to all subsequent visits.
- Remind subjects to promptly report any SAE that may occur at any time during the study.
- Complete the CRF and arrange the next visit.

Visit 09 is the study discharge/end of study visit. At this visit, subjects will be informed about the planned surveillance registry and asked if they wish to participate (ARGOS-SC01_Follow-up) or they will return to standard of care. At the start of the study, all patients enrolled in Switzerland will be requested to sign up for an additional follow-up of 2 years. These patients will automatically transition to the ARGOS-SC_Follow-up.

9. STATISTICS

9.1 Statistical design, method and analytical procedures

The primary purpose of this investigation is to assess the performance of the investigational device.

9.1.1 Demographic and baseline characteristics

Demographic characteristics (age, sex, educational level), lens status, anti-glaucoma medication, and other previous and concurrent treatments will be tabulated for the safety set.

9.1.2 Subject Disposition

The number and percentage of screened, enrolled and implanted subjects, as well as those who complete the follow-up will be tabulated for the safety set. The number and percentage of screen failures and early withdrawals will also be tabulated, along with the reason for the screen failure or drop-out.

9.1.3 Safety Analysis

The incidence and nature of adverse events observed within the safety population will be analyzed by descriptive and explorative statistical methods.

Safety will be described in detail by frequency, seriousness, severity, nature and duration of events. Number of adverse events as well as the number and relative frequency of patients reporting adverse events will be tabulated by system organ class and preferred terms. The same table will be prepared for serious adverse events. In addition, the number and relative frequency of patients reporting adverse events will be tabulated by system organ class and preferred terms in dependence on the worst severity and worst causal relationship. Furthermore, number of adverse device effects as well as the number and frequency of patients reporting adverse device effects will be tabulated by system organ class and preferred terms and not by event description as stated in the protocol.

9.1.4 Performance Analysis

The probability distribution of the difference of the paired measurements grouped within 1 mmHg will be compared to the primary objective of the accepted 70% of the measurements to agree between +/- 5 mmHg.

9.2 Sample Size Calculation

The sample size calculation was based on the study's dual purpose of establishing safety and comparability of IOP measurements with the ARGOS-SC system to those made with GAT and DCT. IOP measurements will be made with all devices at various time points, resulting in a within individual control for IOP variables. Based on these calculations (performance, safety) and considering possible drop-outs, the exploratory investigation will enroll 24 patients. The minimum number of measurements required to hold the performance claim is approx. 120. With multiple (>8) measurements with either method (ARGOS, GAT) per patient, a sufficient number of paired measurements (in total >>120 measurement pairs) will be available to show equivalence of the methods (primary objective)[2].

9.3 Level of significance and the power of the clinical investigation

Significance level is set to 0.10, Power to 80%.

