8.3.7 Number of subjects required

This exploratory investigation will enroll 24 patients.

The overall recruitment time is expected to last a maximum of 12 months.

Page 58 of 97

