9.5 Pass/fail criteria to be applied to the results of the clinical investigation

This investigation will be considered a success if no more than one of the 24 patients experiencing SADEs during the follow-up period (SADEs evaluated by DSMB) and if 70% of the measurements agree between +/- 5 mmHg (limits of agreement from GAT and ARGOS-SC measurements are between +/- 5 mmHg).

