2.9 Study endpoints

2.9.1 Primary endpoints

Performance:

Level of agreement between measurements made using GAT and the ARGOS-SC system at visit V02 - V09.

The concordance of the intraindividual measurement values of GAT and ARGOS-SC will be indicated by the concordance correlation coefficient r_{ccc} (4.6.1), separate for each visit

Additionally, the absolute difference between the GAT and ARGOS-SC measurement will be scaled in \leq 5mmHg and > 5 mmHg and the frequency distribution will be displayed (4.6.1, Table 2).

The Bland-Altman (mean-difference) plot and a X-Y plot should illustrate the comparison of the two methods (4.6.1, Figure 1).

The level of agreement between Pascal DCT and ARGOS-SC will be evaluated analogously.

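### The alpha of 0.10, the 80% power and the equivalence claim in protocol 9.2 and 9.3 are not properties of the 70% within ±5 mmHg rule that decides success

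*Protocol*

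**What the plan says.** **Error rates and sample size.** Protocol 9.3 is one sentence: "Significance level is set to 0.10, Power to 80" per cent. It gives no hypothesis, endpoint or sidedness. Protocol 9.2 says "The minimum number of measurements required to hold the performance claim is approx. 120", and that "in total >>120 measurement pairs) will be available to show equivalence of the methods (primary objective)[2"; the bracketed number refers to a separate sample-size document. Protocol 8.3.7 says "This exploratory investigation will enroll 24 patients".

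**Decision rule.** Protocol 9.1.4 says the distribution of paired differences "will be compared to the primary objective of the accepted 70% of the measurements to agree between +/- 5 mmHg". Protocol 9.5 makes 70% agreement within ±5 mmHg one of two success conditions (the other concerns SADEs) and adds in parentheses "limits of agreement from GAT and ARGOS-SC measurements are between +/- 5 mmHg".

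**SAP.** For the primary endpoint, section 2.9.1 gives the "concordance correlation coefficient r_{ccc} (4.6.1), separate for each visit", plus Bland-Altman and X-Y plots. The absolute difference is split at 5 mmHg (≤ 5 "and > 5 mmHg and the frequency distribution will be displayed (4.6.1, Table 2"). Section 4.6.1 averages up to three readings per method within a visit and reports the number and percentage of pairs within 5 mmHg. The SAP does not mention 70%. Mock-up Table 2 shows 95% intervals for means but none for this proportion. Section 4.1.4 sets a two-tailed alpha of 0.10 for all tests and 95% for all intervals, and calls p<0.05 significant. The only endpoint tests specified are for VFQ-25 changes (4.6.3). Section 4.1.6 marks equivalence and non-inferiority as not applicable.

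**The concern.** A reader of 9.2, 9.3 and 9.5 together would take the primary performance claim to be a powered equivalence result with a 10% error rate. The rule as written has no such error rate. It compares an observed percentage with 70% and passes if the percentage is at least that high.

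Three further gaps bear on the same decision:

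- Each patient can contribute up to eight visit pairs, and nothing in the SAP deals with their correlation. The mock-up shows the percentage visit by visit; a figure pooled across visits is neither specified nor excluded.
- The parenthesis in 9.5 uses a term that SAP 4.6.1 uses in the Bland-Altman sense, which would be a much stricter criterion.
- SAP 4.1.4 gives three levels that do not match.

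At stake is how a pass may be described in the report. Choices about pooling and intervals should also be fixed before database lock, when SAP 3.2 requires the SAP to be final.

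**Working it through.** **Inputs from the documents.** Reference proportion 0.70 (protocol 9.1.4, 9.5); alpha 0.10 and power 80% (9.3); two-tailed (SAP 4.1.4); 24 patients (9.2); 8 follow-up visits, V02 to V09 (8.1.1); readings averaged within a visit (SAP 4.6.1). This gives at most 24 × 8 = 192 GAT/ARGOS-SC visit pairs, before losses and without the optional 24-hour series.

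**Assumptions.** The documents give neither a true agreement rate nor a within-patient correlation (ICC). Both are varied below.

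**1. The plan's own figure, approx. 120.** One-sample proportion, independent pairs:

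n = [(z_α√(p0(1−p0)) + z_β√(p1(1−p1))) / (p1−p0)]²

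With p0 = 0.70, an assumed p1 = 0.80, z_α = 1.645 and z_β = 0.8416: n = [(1.645 × 0.4583 + 0.8416 × 0.4000) / 0.10]² = 118.9, so 119.

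| Assumed p1 | Alpha | n |
|---|---|---|
| 0.79 | two-sided 0.10 | 149 |
| 0.80 | two-sided 0.10 | 119 |
| 0.81 | two-sided 0.10 | 98 |
| 0.80 | one-sided 0.10 | 86 |
| 0.80 | two-sided 0.05 | 153 |
| 0.81 | two-sided 0.05 | 125 |

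The stated alpha and power may therefore have been used to size this criterion, but more than one set of inputs lands near 120. The basis cannot be inferred from the two documents.

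**2. The rule as written.** 0.70 × 192 = 134.4, so 135 pairs are needed. Exact binomial, independent pairs:

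- P(X ≥ 135) at a true 70% = 0.498
- P(X ≥ 135) at a true 65% = 0.070

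At 120 pairs the bar is 84, and the chance of passing at a true 70% is 0.545.

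**3. Repeated pairs.** Design effect 1 + 7 × ICC, normal approximation with continuity correction, true 65%: mean 124.8, variance 192 × 0.65 × 0.35 × (1 + 7 × ICC).

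| ICC (assumed) | Effective pairs | Chance of passing at a true 65% |
|---|---|---|
| 0 | 192 | 7% |
| 0.05 | 142 | 10% |
| 0.1 | 113 | 13% |
| 0.2 | 80 | 17% |
| 0.3 | 62 | 20% |

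A beta-binomial simulation (24 patients × 8 visits, 200,000 runs) gave 10%, 13%, 17% and 21% for the last four rows. At a true 70% the chance stays near 50% whatever the ICC.

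**4. The parenthesis in 9.5.** For normal differences with zero bias, the largest SD that keeps a share p within ±5 mmHg is 5 / z((1+p)/2):

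- p = 0.70: 5 / 1.036 = 4.82 mmHg
- p = 0.95, as for 95% limits of agreement: 5 / 1.960 = 2.55 mmHg

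Any SD between 2.55 and 4.82 mmHg would meet the 70% rule and fail 95% limits within ±5 mmHg.

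**The case against.** **The study is exploratory.** It is first-in-man and single-arm, with 24 patients. A point-estimate benchmark is a recognised choice here, and marking equivalence as not applicable in the SAP fits that choice. This stands. It means the 70% rule need not change; it does not make 9.2 and 9.3 agree with it.

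**Seventy per cent is the accepted level.** A reader might infer from the 50% figure that the type I error is 50% instead of 10%. The documents do not support that. Protocol 9.1.4 treats 70% as acceptable, no document names it as a null value, and any point-estimate rule passes about half the time at its own threshold. The figure shows only that the 0.10 in 9.3 does not describe this rule.

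**The link may be in the sample-size document.** This also stands. A reader might conclude that approx. 120 is wrong; it is not called wrong here, since 119 follows from one plausible set of inputs. Even if that document supplies the inputs, the SAP still contains no test or bound for the criterion.

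**The parenthesis is only a gloss.** That is the more natural reading: the synopsis and 9.1.4 give only the 70% rule, and 95% limits would make the 70% redundant. It would go too far to say that 9.5 sets two conflicting criteria, but the wording leaves the stricter reading open.

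**Repeated measures are covered by the reference list.** Reference 3 concerns intervals for limits of agreement with several observations per individual. The supplied text does not adopt it, and it does not address the 70% proportion.

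**Conclusion.** The point holds as a should-fix. In the two documents supplied, the alpha, the power and the promise to show equivalence are not attached to the rule that decides the performance claim. That rule passes about 50% of the time at a true 70%. At a true 65% it passes 7% of the time with independent pairs and 10% to 20% at an ICC of 0.05 to 0.3. These figures assume 192 pooled visit pairs with no losses; the true rates and the ICC range are assumptions.

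A reader might go further and infer that success must depend on a lower confidence limit. The documents do not require that. It would be a stricter rule and is the sponsor's choice. With independent pairs and an exact 90% interval, the bar would rise from 135 to 146 of 192, with exact power of 92.6% at an assumed true 80%. Allowing for correlation by the effective number of pairs (two-sided 0.10, normal approximation), power would be about 86%, 78%, 64% and 53% at an ICC of 0.05, 0.1, 0.2 and 0.3. With 24 patients, 80% power would therefore be kept only if the ICC were below about 0.1.

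**What to change.** 1. **Protocol 9.2 and 9.3.** Describe the 70% rule as a descriptive point-estimate benchmark and remove the alpha, power and equivalence statements. Otherwise, state what they apply to and under which assumed true rate and within-patient correlation.
2. **SAP 4.6.1.** Add the pooled V02 to V09 proportion of GAT/ARGOS-SC visit pairs with an absolute difference of at most 5 mmHg, with a patient-clustered confidence interval, reported beside the 70% benchmark. A GEE with small-sample correction or a patient-level bootstrap would serve. Keep the per-visit tables as descriptive.
3. **Protocol 9.5.** Say that the 70% proportion decides and that limits of agreement are reported descriptively, or reword the parenthesis so that it cannot be read as a 95% limits criterion.
4. **SAP 4.1.4.** Align the alpha, the interval width and the level at which a result is called significant.

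**Cost.** Wording in both documents and one added interval. If the statements are removed, the study gives up the claim of a powered equivalence result. The pass/fail decision on the 70% rule, the number of patients and the measurements do not change.

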9.4 Expected drop-out rates

The drop-out rate for this study following implantation is expected to be low. The ARGOS-SC is intended to remain in situ and the patient population generally requires close follow-up care by the ophthalmologist. Subjects who do not undergo implantation of an ARGOS-SC will be replaced.

9.5 Pass/fail criteria to be applied to the results of the clinical investigation

This investigation will be considered a success if no more than one of the 24 patients experiencing SADEs during the follow-up period (SADEs evaluated by DSMB) and if 70% of the measurements agree between +/- 5 mmHg (limits of agreement from GAT and ARGOS-SC measurements are between +/- 5 mmHg).

9.6 Interim analysis

One interim analysis is planned for this study. It will take place when all patients have completed the first 6 months of the follow-up period.

9.7 Criteria for termination of the clinical investigation

The participation of an individual site in the study will be discontinued if the sponsor, the investigator or the responsible ethics committee deems it necessary for any reason.

The complete study will be discontinued:

- If the sponsor and/or any responsible regulatory authority or ethic committee judges it necessary for any reason. See also Section 8.3.3 Discontinuation or Withdrawal Criteria Early Patient Withdrawal and Section 12.11 Criteria for Suspension and Premature Termination of Study
- If, throughout the course of the study, the DSMB comes to the conclusion that further implantation of the ARGOS-SC pressure sensor would subject study patients to undue risk

Patients who already have an ARGOS-SC pressure sensor implanted by the time of premature termination will continue to be followed up. If the study is discontinued for safety reasons it will be

proven whether explantation of all ARGOS-SC sensors deems necessary or follow-up of patients is sufficient.

9.8 Procedures for reporting of deviations from the original statistical plan

Significant deviations from the original statistical analysis plan will be listed and clarified in the final clinical investigation report.

9.9 Specification of Subgroups for Analysis

In order to permit investigation of their impact on performance and safety, information will be collected prospectively on the following variables:

- Gender
- Post-surgical complications
- Successful implantation
- Age groups
- Country of investigational site
- Educational level

- Medical History (primary underlying ophthalmic illness or injury necessitating the non-penetrating glaucoma surgery)
- Pre-treatment
- Concomitant medications

Which subgroup analyses are actually performed will be decided at a final data review meeting preceding the statistical analysis, based on the actual distribution of subjects in the study population.

9.10 Treatment of missing, unused and spurious data, including drop-outs and withdrawals

All data of the patients will be used as available. All analyses will be performed on observed cases only. Missing data will not be replaced. Implausible values will be only excluded from the analysis if reasonable. The reason for exclusion will be given in the footer of the table or description of the figure. Patients terminating the trial prematurely due to whatever reason will be evaluated like any patient completing the trial as per protocol, within the analysis sets they qualify for.

Subjects who dropped out during a scheduled visit will be counted for that visit.

9.11 Datasets to be analyzed

9.11.1 Safety set

The safety population comprises all subjects for whom ARGOS-SC pressure sensor implantation was attempted, defined as introduction of the ARGOS-SC pressure sensor into the eye, whether or not the implantation was successful.

9.11.2 Per protocol set

The Per Protocol Set (PPS) will comprise all subjects in whom an ARGOS-SC pressure sensor was successfully implanted and for whom the full data set including IOP measurements made in the clinic and safety data according to protocol are available until 3 months (V06) after surgery. Because IOP measurements conducted outside the clinic will be made at varying times under varying conditions, they are not anticipated to be comparable to those made in the clinic and will not be included in the Per-Protocol evaluation of agreement.

Additional information about the drop-outs: all subjects who revoke their consent and agreement preoperatively will be regarded as screen failures and will not be included in the statistical evaluation. All subjects who revoke their consent and agreement postoperatively will be considered withdrawals. Unless the subject also withdrew consent to use their data, they will be evaluated in the safety analysis.

9.12 Number of subjects at each site

It is planned to enroll an approximately equal number of subjects at each site. Due to the small sample size a stratified design / analysis will not have the power to detect center specific treatment effects.

10. DATA MANAGEMENT

10.1 Site Monitoring

The study will be monitored in compliance with the Declaration of Helsinki, ISO 14155, the Clinical Investigation Plan (CIP) and all applicable national and local regulations. All monitoring activities will be conducted by trained and qualified monitors, who will document each individual monitoring visit. In general, during monitoring visits the monitor will ensure that the study is being conducted according to the CIP, ISO 14155, ICH GCP (International Conference on Harmonisation Good Clinical Practice) and other applicable regulations, and will compare the CRF entries to original source data. He/she will also

Page 77 of 97

make sure the informed consent procedure has been appropriately carried out and will ensure that all SAEs have been reported within applicable timeframes. He/she will also ensure that investigational device accountability has been maintained and will, after completion of the study, perform final accountability and arrange return or destruction of investigational products. For each patient lost to follow-up, the monitor will verify if the study center's attempted contacts with the patient, followed by contacts with the patient's family doctor, were adequate.

Detailed monitoring procedures will be described in a separate monitoring plan.

